10.2.6. Complete Remission Rate

Complete remission rate is defined as rate of CR according to modified IWG AML response criteria.

Number and percentage of subjects with complete remission will be summarized by treatment arm. Comparisons between two treatment arms will be analyzed by Fisher's exact test if chi-square test is not appropriate.

10.2.7. Hematologic Improvement Rate

Hematologic improvement rate is defined as rate of neutrophil response (hematologic improvement neutrophil response [HI-N]) + platelet response (hematologic improvement platelet response [HI-P]) + erythroid response (hematologic improvement erythroid response [HI-E]) according to IWG MDS HI criteria ([Section 17.5](#)).

Number and percentage of subjects with hematologic improvement will be summarized by treatment arm for Phase 2. Comparisons between two treatment arms will be analyzed by Fisher's exact test.

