### 9.1. Overview

This is a Phase 1b/2, multicenter, randomized, study to evaluate the safety and efficacy of oral AG-120 or AG-221 administered with subcutaneous azacitidine versus azacitidine alone in subjects with newly diagnosed acute myeloid leukemia (AML) with an IDH1 or IDH2 mutation. The Phase 1b Stage will be an open-label, combination dose-finding and dose expansion study that will evaluate the safety and clinical activity of oral AG-120 or AG-221 administered with subcutaneous azacitidine in subjects with newly diagnosed AML with an IDH1 or IDH2 mutation. The Phase 2 AG-221 Randomized Stage of the study will be an open label randomized 2-arm design to evaluate the efficacy and safety of oral AG-221 administered with SC azacitidine versus azacitidine alone in subjects with newly diagnosed AML who are not candidates to receive intensive IC and have IDH2 mutations. Phase 1b segment will determine the recommended combination dose (RCD) of AG-120 and AG-221 with azacitidine separately. RCD of AG-120 administered with azacitidine will be used in the Phase 1b AG-120 expansion stage RCD of AG-221 administered with azacitidine will be used in Phase 2 AG-221 randomized stage of the study.

All data will be summarized by study stage. In the analysis of the Phase 1b data, the results will be presented by dose cohort. In the analysis of the Phase 2 data, the results will be presented by 2 arms: AG-221 + azacitidine and azacitidine mono therapy. The statistical comparisons will be conducted for AG-221 + azacitidine versus azacitidine mono therapy. In addition, where appropriate, a total column will be included to summarize subjects across cohorts/treatment groups. Summaries of continuous variables will present the number of subjects included in the analysis (N), the mean and standard deviation (SDev), the median, the minimum and the maximum values. Counts and percentages will be presented in summaries of categorical variables. The denominator for each percentage will be the number of subjects in the population cohort/treatment group unless otherwise specified. In general, missing data will not be imputed unless otherwise specified.

All statistical analyses specified in this protocol will be conducted using SAS® Version 9.2 or higher unless otherwise specified.

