10.2. Analyses of Secondary Efficacy Endpoints

For Phase 1b, ORR and Sponsor Derived CR/CRh (based on laboratory dataset) are secondary efficacy endpoints and will be analyzed based on the FAP population and on the EAP as sensitivity analysis. These endpoints will be presented descriptively with 95% and 90% CI. Other measures of clinical activity, including duration of response, duration of CR/CRh, duration of remission, time to response, time to remission, time to CR/CRh, event-free survival (EFS), and overall survival may be summarized as appropriate in the FAP population.

For Phase 2, time-to-event secondary efficacy variables are displayed as part of [Table 2](#) (EFS, duration of response, OS, duration of remission (CR), and duration of sponsor assessed CR and CRh) will be analyzed by the KM method if appropriate to estimate time-to-event curves. In addition, Cox proportional hazards regression models will be generated to obtain hazard ratios and their two-sided 95% CI, and the p-value will be based on 2-sided log-rank test as appropriate. Time to response, time to remission, and time to sponsored assessed CR and CRh will be summarized

descriptively. Counts and percentages will be used to describe categorical variables. Rates, such as Complete remission rate, Hematologic improvement rate, sponsor derived CR and CR + CRh, will be analyzed similarly to ORR. All secondary efficacy endpoints for Phase 2 will be analyzed based on ITT population and on the mITT as supportive evidence and to assess the robustness of the efficacy findings. Subjects will be analyzed according to randomized treatment arm.

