Progressive Disease (PD)^a	Defined as one of the following conditions: 
 For subjects with 5 to 70% BM blasts at baseline: a $> 50\%$ increase of BM blast count percentage from baseline to $\geq 20\%$; or For subjects with $> 70\%$ BM blasts at baseline: a doubling of absolute blast count in PB from baseline to $\geq 10 \times 10^9/L$ (10,000/μL); or Development of new extramedullary disease since last response assessment 
Progressive disease is to be confirmed by 2 consecutive response assessments separated by at least 1 month. The date of progressive disease is defined as the first date that one of three conditions listed above was met.

AML = acute myeloid leukemia; ANC= absolute neutrophil count; BM= bone marrow; PB=peripheral blood;;IWG= International Working Group. CRh= morphologic complete remission with partial hematologic recovery: defined as less than 5% blasts in a BM aspirate sample with marrow spicules plus ANC $> 0.5 \times 10^9/L$ (1,000/ μ L) & Platelet count $> 50 \times 10^9/L$ (100,000/ μ L).

^a Modification to IWG response criteria.

^b If the pre-treatment BM blast percentage was 50% to 100%, the percentage of blasts must decrease to a value between 5% and 25%; if the pre-treatment blast percentage was 20% to less than 49%, they must decrease by at least half to a value of more than 5%.

Notes: Deletions to the IWG response criteria are not shown.

17.5. Hematologic Improvement According to the International Working Group for Myelodysplastic Syndromes

Hematologic Improvement According to IWG Criteria	
Hematologic improvement ^a	Response criteria (responses must last at least 8 week) ^b
Erythroid Response (HI-E) (pre-treatment, < 11 g/dL)	
 Hemoglobin increase by ≥ 1.5 g/dL Relevant Reduction in units of RBC transfusions by an absolute number of at least 4 RBC transfusions/8 week compared with the pretreatment transfusion number in the previous 8 weeks 
Note: Only RBC transfusions given for a hemoglobin of ≤ 9.0 g/dL on treatment will count in the RBC transfusion response evaluation^b

Platelet Response (HI-P) (pre-treatment, < $100 \times 10^9/L$)	
 Absolute increase of $\geq 30 \times 10^9/L$ for subjects starting with $> 20 \times 10^9/L$ platelets Increase from $< 20 \times 10^9/L$ to $> 20 \times 10^9/L$ and by at least 100%^b

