Neutrophil Response (HI-N) (pre-treatment, < $1.0 \times 10^9/L$)	
 At least 100% increase and an absolute increase $> 0.5 \times 10^9/L$^b
Progression or Relapse After HI ^c	
At least 1 of the following:
 
 At least 50% decrease from maximum response levels in granulocytes or platelets Reduction in hemoglobin by ≥ 1.5 g/dL Transfusion dependence

HI-E = hematologic improvement erythroid response; HI-N = hematologic improvement neutrophil response; HI-P = hematologic improvement platelet response; IWG = International Working Group; RBC = red blood cell.

Pre-treatment counts averages of at least 2 measurements (not influenced by transfusions, ie, no RBC transfusions for 2 weeks and no platelet transfusions for 1 week) ≥ 1 week apart (modification).

Modification to IWG [REDACTED] response criteria.

^c In the absence of another explanation, such as acute infection, repeated courses of chemotherapy (modification), gastrointestinal bleeding, hemolysis, and so forth. It is recommended that the 2 kinds of erythroid and platelet responses be reported overall as well as by the individual response pattern.

Note: Deletions to the IWG response criteria are not shown. To convert hemoglobin levels from grams per deciliter to grams per liter, multiply grams per deciliter by 10.

[REDACTED]

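### The hematologic improvement rate counts subjects who cannot meet its definition as non-responders, which dilutes the rate and the difference but does not bias the comparison

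*SAP*

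**What the plan says.** SAP 10.2.7 defines the endpoint as a composite: "Hematologic improvement rate is defined as rate of neutrophil response (hematologic improvement neutrophil response [HI-N]) + platelet response", plus erythroid response. The planned output is one line: "Number and percentage of subjects with hematologic improvement will be summarized by treatment arm for Phase 2", with a Fisher exact test between arms. No denominator is given there.

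Two other places fill the gap. SAP 10.2: "All secondary efficacy endpoints for Phase 2 will be analyzed based on ITT population and on the mITT as supportive evidence". Protocol 9.1: "The denominator for each percentage will be the number of subjects in the population cohort/treatment group unless otherwise specified". Nothing specifies otherwise for HI, so the denominator is every randomized subject in the arm.

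SAP 17.5 and Protocol Appendix G attach a pre-treatment condition to each lineage. The erythroid row begins "Erythroid Response (HI-E) (pre-treatment, < 11 g/dL"; the platelet row requires a count below 100 x 10^9/L and the neutrophil row an ANC below 1.0 x 10^9/L.

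Entry (Protocol 4.2) requires at least 20% marrow blasts but no cytopenia. Protocol 7.2.2.3.4 provides for subjects without reduced baseline counts (ANC at least 1.5 and platelets at least 75 x 10^9/L among its conditions); such a subject lies above the neutrophil threshold.

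**The concern.** A subject above a lineage's threshold cannot score a response in that lineage, whatever the drug does. A subject above all three cannot score HI at all, yet enters the percentage and the Fisher test as a failure. The reported rate therefore mixes drug effect with the share of subjects who were cytopenic at entry, and the absolute difference between arms is smaller than among those who could respond.

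The SAP treats a neighbouring measure differently. Section 8.5 summarizes transfusion independence by baseline dependence status and tabulates the change among subjects dependent at baseline. HI has no such conditioning.

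At stake are the size and precision of one secondary endpoint. The primary ORR analysis is not affected.

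**Working it through.** **Inputs from the documents.** 66 v 33 subjects, 2:1 (SAP 4.4); Fisher's exact test (SAP 10.2.7); stratification by primary or secondary AML only (SAP 4.3). The level for HI can be read as two-sided 0.05 (SAP 10, general rule) or 0.2 (SAP 10.2 says rates are analysed like ORR), so both are shown.

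**Assumptions.** The documents give no HI rate and no baseline cytopenia share. I assume HI of 30% v 50% among eligible subjects, borrowing the ORR design rates, and vary the eligible share e from 0.50 to 0.95. I read the plus signs as any-lineage, as they are used for ORR; SAP 10.2.7 does not say so.

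**The plan's own figure.** The only stated power is 75% for ORR. Pooled rate = (33 x 0.30 + 66 x 0.50)/99 = 0.433. SE under the null = sqrt(0.433 x 0.567 x (1/33 + 1/66)) = 0.1057; under the alternative = sqrt(0.21/33 + 0.25/66) = 0.1008. Power = Phi((0.20 - 1.2816 x 0.1057)/0.1008) = 73.9%. Exact enumeration of the chi-square test gives 75.3%, so the figure reproduces. Fisher's test with the same inputs gives 69.7%.

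**Dilution.** Reported rate = e x (HI rate among eligible). The risk difference becomes e x 20 points; the ratio of rates is unchanged (at e = 0.60, 30/18 = 50/30).

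**Exact Fisher power**, all-ITT v eligible-only, with eligible numbers fixed at their rounded expectation (control v combination):

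| e | Eligible n | All-ITT rates | Difference, points (ITT v eligible) | Power at 0.2 | Power at 0.05 |
|---|---|---|---|---|---|
| 0.95 | 31 v 63 | 28.5% v 47.5% | 19 v 20 | 67% v 70% | 41% v 43% |
| 0.80 | 26 v 53 | 24% v 40% | 16 v 20 | 57% v 60% | 32% v 34% |
| 0.60 | 20 v 40 | 18% v 30% | 12 v 20 | 43% v 55% | 21% v 25% |
| 0.50 | 16 v 33 | 15% v 25% | 10 v 20 | 39% v 45% | 17% v 21% |

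Part of these gaps is the discreteness of Fisher's test. A smoother guide at e = 0.60 is the expected z:

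- All ITT: 0.12/sqrt(0.30 x 0.70/66 + 0.18 x 0.82/33) = 0.12/0.0875 = 1.37.
- Eligible only: 0.20/sqrt(0.25/39.6 + 0.21/19.8) = 0.20/0.1301 = 1.54.

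At two-sided 0.2 these give Phi(1.37 - 1.28) = 54% and Phi(1.54 - 1.28) = 60%, a gap of about 6 points against 12 from the Fisher enumeration.

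**Chance imbalance in eligibility.** SD of the between-arm difference in eligible share = sqrt(e(1-e)(1/33 + 1/66)). The 95% range is +/-9 points at e = 0.95, +/-17 at 0.80 and +/-20 at 0.60. With a common 40% HI rate among eligible subjects, that moves the HI difference by +/-3.6, +/-6.7 and +/-8.2 points.

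This is not extra error. At e = 0.60 and 50% HI in both arms, the per-subject variance of the all-ITT outcome is 0.30 x 0.70 = 0.21. It splits into 0.60 x 0.25 = 0.15 from response among eligible subjects and 0.25 x 0.24 = 0.06 from eligibility. The second part gives sqrt(0.06 x (1/66 + 1/33)) = 5.2 points, already inside the full SE of sqrt(0.21 x (1/66 + 1/33)) = 9.8 points.

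**Type I error.** With a common 40% HI rate among eligible subjects and e of 0.95, 0.80 and 0.60, the all-ITT Fisher test has exact size 0.179, 0.171 and 0.156 at nominal 0.2, and 0.040, 0.039 and 0.036 at nominal 0.05.

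**The case against.** The strongest defence is that all-ITT is a valid and conservative choice, and is the SAP's stated policy for every Phase 2 secondary efficacy endpoint. Randomization makes the dilution equal in expectation. SAP 10.2.7 plans one test, of a composite, for which only a subject above all three thresholds is excluded from responding; if nearly everyone has some cytopenia, about 1 point in 20 is lost. All of this stands. It limits the weight of the point but does not make the denominator a good match to the definition.

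Baseline imbalance is also partly visible already: SAP 8.2.1 tabulates platelets with a cut at 100 x 10^9/L and ANC with a cut at 1.0 x 10^9/L. That also stands, but the hemoglobin cut is 80 g/L rather than 110 g/L, and the number eligible for at least one lineage is not shown.

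A reader might infer two stronger things. One is that chance imbalance in baseline counts adds a spurious difference or undermines the test. It does not: the variance split shows that this variation is already in the ordinary standard error, and the test keeps its size. The other is that the SAP 17.5 footnote requires single-lineage rates, where dilution would be greatest, because it wants responses "reported overall as well as by the individual response pattern". The footnote concerns the two kinds of erythroid and platelet response, most naturally the two criteria listed within each of those lineages, and does not address denominators.

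**Conclusion.** The point holds as an attenuation problem. Read together, SAP 10.2.7, SAP 10.2 and Protocol 9.1 count subjects who cannot meet the SAP 17.5 definition as non-responders. The reported rate and risk difference are multiplied by the eligible share, and some power is lost; eligible-only power was at least as high at every share examined. The documents do not support a claim of systematic bias between arms or of inflated type I error.

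The size depends on an eligible share that the documents do not give. On the assumed HI rates it is small for the planned composite if most subjects are cytopenic (19 v 20 points at 95%) and material at 60% (12 v 20 points), or for any single-lineage rate with a similar share. SAP 10.2.7 plans no between-arm test by lineage. The endpoint is secondary, so this is a desirable improvement, not a necessary one.

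**What to change.** In SAP 10.2.7, state that the arms are compared on HI among ITT subjects who meet at least one SAP 17.5 threshold before treatment, and that any lineage rate uses subjects who meet that lineage's threshold. Show the eligible number per arm and keep the all-ITT percentage as a second line. Eligibility is fixed before treatment, and eligible subjects who are never treated stay in as non-responders, so the randomized comparison is preserved.

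The wording must name the baseline, because two are in play. SAP 17.5 uses the average of at least two counts, at least a week apart and free of transfusion influence; SAP 5.1 uses the last non-missing value before treatment. Use the SAP 17.5 average where it exists and the SAP 5.1 value otherwise. Requiring the average alone would drop recently transfused subjects, some of whom could respond through reduced transfusion need. Also say that response in any one lineage is enough.

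The cost is one baseline flag and a few sentences. The downside is a smaller sample and a wider interval for the absolute difference: at e = 0.60 its SE rises from 8.7 to 13.0 points, although z still improves. The protocol's justification for amendment says that the primary analysis report is already final, so results on the new denominator should be labelled supplementary.

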10.2.8. Time to Response

Time to response is defined as time from the first dose of study drug for Phase 1b subjects and the date of randomization for Phase 2 subjects to the first documented CR/CRi/CRp/PR/MLFS according to modified IWG AML response criteria.

Time to response will be analyzed using the summary statistics for each treatment arm. Only subjects with documented CR/CRi/CRp/PR/MLFS response as determined by investigator assessment will be included in the analysis.

10.2.9. Time to Remission

Time to remission is defined as time from the first dose of study drug for Phase 1b subjects and the date of randomization for Phase 2 subjects to the first documented CR according to modified IWG AML response criteria.

Time to remission will be analyzed using the summary statistics for each treatment arm. Only subjects with documented CR as determined by investigator assessment will be included in the analysis.

10.2.10. Sponsor Derived CR

Sponsor derived CR rate is defined as rate of CR based on laboratory data.

Number and percentage of subjects with sponsor derived complete remission will be summarized by treatment arm. Comparisons between two treatment arms will be analyzed by Fisher's exact test.

10.2.11. Sponsor Derived CR and CRh

Sponsor derived CR and CRh rate is defined as rate of CR and CRh based on laboratory data. CRh is defined as less than 5% blasts in a BM aspirate sample with marrow spicules plus ANC > 0.5 x 10⁹/L (1,000/ μ L) & Platelet count > 50 x 10⁹/L (100,000/ μ L).

Number and percentage of subjects with sponsor derived CR and CRh will be summarized by treatment arm. Comparisons between two treatment arms will be analyzed by Fisher's exact test.

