Not evaluable (NE)a	Defined as without a post-treatment response assessment
Stable Disease (SD)a	Defined as failure to meet any of the above criteria and not meeting the criteria of progressive disease (see below)
Progressive Disease (PD)a	Defined as one of the following conditions: 
 
For subjects with 5 to 70% BM blasts at baseline: a <math>> 50\%</math> increase of BM blast count percentage from baseline to <math>\geq 20\%</math>; or
 
For subjects with <math>> 70\%</math> BM blasts at baseline: a doubling of absolute blast count in peripheral blood from baseline to <math>\geq 10 \times 10^9/L</math> (10,000/<math>\mu</math>L); or
 
Development of new extramedullary disease since last response assessment
 
 Progressive disease is to be confirmed by 2 consecutive response assessments separated by at least 1 month. The date of progressive disease is defined as the first date that one of three conditions listed above was met.

AML = acute myeloid leukemia; ANC = absolute neutrophil count; BM = bone marrow; IWG = International Working Group. CRh = morphologic complete remission with partial hematologic recovery: defined as less than 5% blasts in a BM aspirate sample with marrow spicules plus ANC  $> 500 \times 10^9/L$  (1,000/ $\mu$ L) & Platelet count  $> 50 \times 10^9/L$  (100,000/ $\mu$ L).

a Modification to IWG response criteria.

b If the pre-treatment bone marrow blast percentage was 50% to 100%, the percentage of blasts must decrease to a value between 5% and 25%; if the pre-treatment blast percentage was 20% to less than 49%, they must decrease by at least half to a value of more than 5%.

Notes: Deletions to the IWG response criteria are not shown.

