17.4. International Working Group Acute Myeloid Leukemia Response Criteria

Hematologic Response According to modified IWG Criteria for AML	
Category	Definition
Morphologic Complete Remission (CR)	Defined as less than 5% blasts in a BM aspirate sample with marrow spicules and with a count of at least 200 nucleated cells. There should be no blasts with Auer rods and absence of extramedullary disease. Plus, all the following conditions should be met: 
 ANC $\geq 1 \times 10^9/L$ (1,000/μL) Platelet count $\geq 100 \times 10^9/L$ (100,000/μL) Independent of red cell transfusions for ≥ 1 week immediately before each response assessment
Morphologic Complete Remission with Incomplete Neutrophil Recovery (CRi)^a	Defined as all criteria of morphologic CR except the following: 
 ANC $< 1 \times 10^9/L$ (1,000/μL)
Morphologic Complete Remission with Incomplete Platelet Recovery (CRp)^a	Defined as all criteria of morphologic CR except the following: 
 Platelet count $< 100 \times 10^9/L$ (100,000/μL)
Morphologic Leukemia-free State (MLFS)	Defined as less than 5% blasts in a BM aspirate sample with marrow spicules and with a count of at least 200 nucleated cells. There should be no blasts with Auer rods and absence of extramedullary disease
Partial Remission (PR)	Defined as all hematologic criteria of morphologic CR with a $> 50\%$ decrease in the percentage of BM blasts to 5% to 25% (a blast count value of $< 5\%$ may also be considered a partial remission if Auer rods are present) ^b
Cytogenetic Complete Remission (CRc)	Defined as CR/CRi/CRp with a reversion to a normal karyotype in cases with an abnormal karyotype at baseline, based on evaluating ≥ 20 metaphase cells from BM
Morphologic Relapse after CR/CRi/CRp^a	Defined as one of the following conditions: 
 Reappearance of $\geq 5\%$ blasts in the BM not attributable to any other cause (eg, BM regeneration after consolidation therapy); or Development of extramedullary disease
Not evaluable (NE)^a	Defined as without a post-treatment response assessment
Stable Disease (SD)^a	Defined as failure to meet any of the above criteria and not meeting the criteria of progressive disease (see below)

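### CRh omits the Auer-rod, extramedullary-disease and 200-cell conditions that CR and MLFS carry, so a visit the same table calls PD, PR or stable disease can count as CRh

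*SAP*

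**What the plan says.** CRh is defined in three places, each time with the same elements.

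- SAP 10.2.11: "CRh is defined as less than 5% blasts in a BM aspirate sample with marrow spicules plus ANC" and platelet floors.
- SAP 17.4, note under the response table: "defined as less than 5% blasts in a BM aspirate sample with marrow spicules plus ANC" and platelet floors.
- Protocol Appendix F, note under the response table: "morphologic complete remission with partial hematologic recovery: defined as less than 5% blasts in a BM aspirate sample with marrow spicules", followed by the two counts.

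The remission categories in SAP 17.4 ask for more. CR and MLFS need an aspirate "with marrow spicules and with a count of at least 200 nucleated cells", and for both the table adds: "There should be no blasts with Auer rods and absence of extramedullary disease". CRi and CRp take these conditions over because each is "Defined as all criteria of morphologic CR except the following" for one count. CRh has no such link, no upper limit on counts, and no rule that a visit assessed as PR, stable disease or PD cannot be CRh.

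Two other rows matter. Under PR, a marrow with fewer than 5% blasts "may also be considered a partial remission if Auer rods are present", provided the hematologic criteria of CR are met. Under PD, one of three alternative conditions is "Development of new extramedullary disease since last response assessment". PD must be confirmed at least a month later, but is dated to the first visit that met the condition.

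SAP 10.2.11 bases the derivation on laboratory data, and Protocol 9.6.2 says the investigator assessment does not supply CRh.

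**The concern.** On clearance of disease, CRh is looser than MLFS, although its name describes a complete remission with partial count recovery. A programmer who follows SAP 10.2.11 literally has no instruction to look at extramedullary disease or Auer rods. There is no second source for CRh that would expose a conflict with the investigator's assessment.

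At stake are three Phase 2 secondary endpoints (CR+CRh rate, time to CR/CRh, duration of CR/CRh) and the sponsor-derived CR/CRh endpoint of Phase 1b. The Phase 2 rate is compared between arms under SAP 10.2.11. The primary endpoint, ORR, does not include CRh and is assessed by the investigator. EFS is also assessed by the investigator, and OS depends only on death. None of these three is touched.

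**Working it through.** There is no stated figure to reproduce. The check applies the SAP 17.4 rules and the SAP 10.2.11 CRh rule to test visits.

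Every visit has 3% marrow blasts, spicules and no red-cell transfusion in the past week. Unless noted, 250 cells were counted, ANC is 1.5 and platelets are 150 (both x10^9/L).

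| Visit | CR | MLFS | Other category | CRh as written | CRh or CR after the fix |
|---|---|---|---|---|---|
| Clean | yes | yes | none | yes | yes (as CR) |
| New extramedullary disease | no | no | PD once confirmed, dated to this visit | yes | no |
| Persisting extramedullary disease | no | no | stable disease | yes | no |
| Auer rods, ANC 1.5, platelets 150 | no | no | PR allowed | yes | no |
| Auer rods, ANC 0.7, platelets 70 | no | no | stable disease | yes | no |
| 100 cells counted | no | no | no PD or PR follows | yes | no |
| Clean, ANC 0.7, platelets 70 | no | yes | none | yes | yes (as CRh) |

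**Count cut-offs.** The SAP prints an ANC floor of 0.5 x10^9/L, which is 500/µL, beside 1,000/µL. It prints a platelet floor of 50 x10^9/L, which is 50,000/µL, beside 100,000/µL. The visits at ANC 1.5 and platelets 150 give the same result under either set; the two visits at 0.7 and 70 are CRh only under the first. Protocol Appendix F prints an ANC floor of 500 x10^9/L, which no test visit would meet. That is a separate defect, and this point does not rest on it.

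**PD overlap.** It arises through new extramedullary disease. The marrow-blast route needs at least 20% blasts and cannot coincide with fewer than 5%. The peripheral-blood route is not formally excluded, but nothing here relies on it.

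**PR overlap.** It arises only through the Auer-rod clause and only at CR-level counts, and it exists because CRh has no upper count limit. Between the CRh and CR counts the Auer-rod visit is stable disease.

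**Effect on the endpoints.** Under SAP 10.2.12, duration runs from first CR/CRh to relapse, PD or death. If the first CRh visit is also the date of a confirmed PD, start and end coincide and the interval has no length. The subject still counts in the rate and contributes a time to CR/CRh. A subject admitted through an Auer-rod visit enters all three endpoints from that visit.

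**Size per subject.** For a subject with no other qualifying visit: 1/66 = 1.5 points in the AG-221 arm and 1/33 = 3.0 points in the azacitidine arm.

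**The case against.** The name of the category is the best defense. CRh is spelled out as a morphologic complete remission with partial hematologic recovery, and its definition sits under a table that sets out morphologic CR in full. It may be shorthand that takes the CR morphology for granted. That is plausible, but neither document says so, whereas CRi and CRp are tied to CR expressly. If it was intended, the fix only writes it down.

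Several stronger readings are tempting, and the documents do not support them:

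- A reader might infer that any Auer-rod visit counted as CRh is a PR. PR needs CR-level counts, and the clause is permissive.
- A reader might infer that a single visit with new extramedullary disease is already PD, and that a remission clock then runs on in a subject who has failed. PD needs confirmation; once confirmed it is back-dated, so the interval is zero.
- A reader might infer that the 200-cell omission also lets PD or PR through. It concerns only whether the sample is adequate.
- A reader might assume that 2-5% of subjects have such findings and conclude that 1-3 subjects in Arm 1 and 1-2 in Arm 2 are misclassified. That treats prevalence as misclassification. The finding must occur at a visit with a clear marrow and adequate counts, in a subject with no clean CR or CRh visit at any time.

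Two further objections stand. Sponsor-derived CR (SAP 10.2.10) also rests on laboratory data, so how extramedullary disease enters is unclear there too. And no visible passage shows extramedullary disease or Auer rods as separately recorded fields, so one cannot assume that they are simply another input.

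**Conclusion.** The CRh rule is wrong as written, with consequences confined to secondary endpoints. All three definitions omit conditions that every neighboring remission category carries. Followed literally, they count as CRh a visit with new extramedullary disease or with Auer rods, in a rate that is compared between arms.

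The effect is 1.5 or 3.0 points per subject with no other qualifying visit. How many subjects that is cannot be computed, because the documents give no frequency of either finding. As an illustration only, assume 2-5% of subjects have one, independence, and the planning ORRs of 50% and 30% as a rough proxy for a clear marrow with adequate counts:

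- AG-221 arm: 66 x 0.02 x 0.5 = 0.7 to 66 x 0.05 x 0.5 = 1.7 subjects.
- Azacitidine arm: 33 x 0.02 x 0.3 = 0.2 to 33 x 0.05 x 0.3 = 0.5 subjects.

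Requiring no clean visit elsewhere lowers these further, so the number is probably very small. The reason to act is that the rule is wrong and cheap to correct, not that a large bias has been shown.

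**What to change.** In SAP 10.2.11, SAP 17.4 and Protocol Appendix F, define CRh as all MLFS criteria plus the CRh ANC and platelet thresholds, not meeting CR. In the table above this removes every conflicting visit and keeps both clean ones.

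In SAP 10.2.10 and 10.2.11, state that the sponsor derivation of both CR and CRh uses the extramedullary and Auer-rod findings behind the investigator's response assessment. Where these are not separately recorded, state that a visit the investigator assessed as PD or relapse cannot be CR or CRh. This fallback is partial: it does not catch an Auer-rod visit assessed as PR or stable disease.

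The amendment justification in the Protocol says the primary report was final by 15 Dec 2020. In practice the work is therefore to correct the text, check the subjects counted as CRh against the investigator's assessment at the same visit, and report any change.

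The cost is one sentence in each definition and a change to the derivation, larger if the findings have to be retrieved from source. The CR+CRh rate may fall slightly, and the derivation is no longer purely laboratory-based.
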